- Listing to be sorted by increasing CPX-POM dose.

Sponsor: CicloMed
Protocol: CPX-POM-001
Statistical Analysis Plan
(TFL shells):
Version 1.0 / 02FEB2018

Protocol: CPX-POM-001

--- DELIVERY TYPE ---

Page 1 of X

Listing 16.2.3-2 - HIV, Hepatitis and Pregnancy Test Results
 (All Patients)

Center/ Patient	CPX-POM Dose group	Visit	Parameter	Assessment Performed?	Assessment Date	Study Day	Result
XXXX	30 mg/m ²	SCR	HIV	Yes	DDMMYYYY	XX	No
			Hepatitis A	Yes	DDMMYYYY	XX	No
			Hepatitis B	Yes	DDMMYYYY	XX	No
			Hepatitis C	Yes	DDMMYYYY	XX	No
			Pregnancy Test	Yes	DDMMYYYY	XX	No
		BAS	Pregnancy Test	Yes	DDMMYYYY	XX	No

<repeat for Day 1 of next cycles if relevant>
<cont.>

Program: (Program name.sas) (run on: DDMMYYYY HH:MM)

Filename: (Specify file name.rtf)

PROGRAMMING NOTES:

- Listing to be sorted by increasing CPX-POM dose.

Sponsor: CicloMed
Protocol: CPX-POM-001
Statistical Analysis Plan
(TFL shells):
Version 1.0 / 02FEB2018

Sponsor: CicloMed
Protocol: CPX-POM-001
Statistical Analysis Plan
(TFL shells):
Version 1.0 / 02FEB2018

Protocol: CPX-POM-001

--- DELIVERY TYPE ---

Page 1 of X

Listing 16.2.4-1 - Cancer History
 (All Patients)

Center/ Patient	CPX-POM Dose group	Cancer Type	If Other, specify	Initial Diagnosis Date (Day)	Disease Stage at Initial Diagnosis	Current Disease Stage	Pres. of Metas.?	Date of Metastatic Diagnosis (Day)	Location	If Other, specify
XXXX	30 mg/m ²	XXXXX		DDMMYYYY (XXX)	Grade X	Grade X	No			
XXXX	[D2] mg/m ²	XXXXX		DDMMYYYY (XXX)	Grade X	Grade X	No			
XXXX	[D3] mg/m ²	XXXXX		DDMMYYYY (XXX)	Grade X	Grade X	Yes	DDMMYYYY (XXX)	Bone	
XXXX	[D4] mg/m ²	XXXXX		----YYYY	Grade X	Grade X	No			
XXXX	[D4] mg/m ²	Other	XXXXX	DDMMYYYY (XXX)	Grade X	Grade X	Yes	DDMMYYYY (XXX)	Other	XXXXX
XXXX	[D4] mg/m ²	XXXXX		----YYYY	Grade X	Grade X	Yes	DDMMYYYY (XXX)	Lungs Liver	

<etc>

Pres.: Presence; Metas.: Mestastases

Day was from the date of first dose of CPX-POM administration. Dates are displayed as DDMMYYYY, -- represents an unknown date component.

Program: (Program name.sas) (run on: DDMMYYYY HH:MM)

Filename: (Specify file name.rtf)

PROGRAMMING NOTES:

- Listing to be sorted by increasing CPX-POM dose.

Sponsor: CicloMed
Protocol: CPX-POM-001
Statistical Analysis Plan
(TFL shells):
Version 1.0 / 02FEB2018

Protocol: CPX-POM-001

--- DELIVERY TYPE ---

Page 1 of X

Listing 16.2.4-2 - Prior Cancer Therapies
 (All Patients)

Center/ Patient	CPX-POM Dose group	Therapy Type	If Radiation, specify	Therapy Name	Line of Therapy	Treatment Setting	Treatment Intent	Start Date (Day) End Date (Day)	Best Response
XXXX	30 mg/m ²	XXXXX		XXXXX	X	XXXXX	XXXXX	DDMMYYYY (XX) DDMMYYYY (XX)	XXXXX
XXXX	[D2] mg/m ²	XXXXX		XXXXX	X	XXXXX	XXXXX	DDMMYYYY (XX) DDMMYYYY (XX)	XXXXX
XXXX	[D3] mg/m ²	Radiation	XXXXX	XXXXX	X	XXXXX	XXXXX	DDMMYYYY (XX) DDMMYYYY (XX)	XXXXX

<etc>

Day was from the date of first dose of CPX-POM administration. Dates are displayed as DDMMYYYY, -- represents an unknown date component.

Program: (Program name.sas) (run on: DDMMYYYY HH:MM)

Filename: (Specify file name.rtf)

PROGRAMMING NOTES:

- Listing to be sorted by increasing CPX-POM dose.

Sponsor: CicloMed
Protocol: CPX-POM-001
Statistical Analysis Plan
(TFL shells):
Version 1.0 / 02FEB2018

Protocol: CPX-POM-001

--- DELIVERY TYPE ----

Page 1 of X

Listing 16.2.4-3 - Other Medical History
 (All Patients)

CPX-POM Dose Group: 30 mg/m²

Center/ Patient	System Organ Class/ Preferred Term/ Verbatim	Start Date (Day)	End Date (Day)	Treated with medication?
XXXX	XXXXXX/ XXXXX/ XXXXXXXXXXXX	DDMMYYYY (XXX)	DDMMYYYY (XXX)	No
XXXX	XXXXXX/ XXXXX/ XXXXXXXXXXXX	--MMYYYY	Ongoing	Yes

<cont.>

Day was from the date of first dose of CPX-POM administration. Dates are displayed as DDMMYYYY, -- represents an unknown date component.

MedDRA <version no.>

Program: (Program name.sas) (run on: DDMMYYYY HH:MM)

Filename: (Specify file name.rtf)

PROGRAMMING NOTES:

- Listing to be sorted by increasing CPX-POM dose.

Sponsor: CicloMed
Protocol: CPX-POM-001
Statistical Analysis Plan
(TFL shells):
Version 1.0 / 02FEB2018

Protocol: CPX-POM-001

--- DELIVERY TYPE ----

Page 1 of X

Listing 16.2.4-4 - Cardiac Function
 (All Patients)

Center/ Patient	CPX-POM Dose group	Echocardiogram or MUGA Scan performed?	Method of Assessment	Date of Assessment	Overall Interpretation	If Abnormal CS, specify
XXXX	30 mg/m ²	Yes	Echocardiogram	DDMMYYYY	XXXXX	
XXXX	[D2] mg/m ²	Yes	MUGA	DDMMYYYY	Abnormal CS	XXXXX
XXXX	[D3] mg/m ²	Yes	Echocardiogram	DDMMYYYY	XXXXX	
<etc>						

CS: Clinically Significant. Dates are displayed as DDMMYYYY, -- represents an unknown date component.

Program: (Program name.sas) (run on: DDMMYYYY HH:MM)

Filename: (Specify file name.rtf)

PROGRAMMING NOTES:

- Listing to be sorted by increasing CPX-POM dose.

Sponsor: CicloMed
Protocol: CPX-POM-001
Statistical Analysis Plan
(TFL shells):
Version 1.0 / 02FEB2018

Protocol: CPX-POM-001

--- DELIVERY TYPE ---

Page 1 of X

Listing 16.2.4-5 - Ophthalmologic Exam
 (All Patients)

Center/ Patient	CPX-POM Dose group	Ophthalmology Assessments performed?	Use of Corrective Lenses?	Date of Assessment	Overall Interpretation	If Abnormal CS, specify
XXXX	30 mg/m ²	Yes	Yes	DDMMYYYY	XXXXX	
XXXX	[D2] mg/m ²	Yes	No	DDMMYYYY	Abnormal CS	XXXXX
XXXX	[D3] mg/m ²	Yes	No	DDMMYYYY	XXXXX	
<etc>						

CS: Clinically Significant. Dates are displayed as DDMMYYYY, -- represents an unknown date component.

Program: (Program name.sas) (run on: DDMMYYYY HH:MM)

Filename: (Specify file name.rtf)

PROGRAMMING NOTES:

- Listing to be sorted by increasing CPX-POM dose.

Listing 16.2.4-6 - RECIST Target Lesions
 (All Patients)

Center/ Patient	CPX-POM Dose group	Visit/ Target Lesions Identified at Screening Visit?	Date of Scans review	Lesion Number	Organ Site	Specific Location within the Organ Site	Lymph Node Type	Method	Lesion Diameter (mm)		
XXXX	30 mg/m ²	C1 TRT D1 / Yes	DDMMYYYY	T01	XXXXX	XXXXX	XXXXX	XXXXX	XXXXX		
				T02	XXXXX	XXXXX	XXXXX	XXXXX	XXXXX		
XXXX	[D2] mg/m ²	C1 TRT D1 / Yes	DDMMYYYY	T01	XXXXX	XXXXX	XXXXX	XXXXX	XXXXX		
				C2 TRT D1 / Yes	DDMMYYYY	T01	XXXXX	XXXXX	XXXXX	XXXXX	XXXXX
					DDMMYYYY	T02	XXXXX	XXXXX	XXXXX	XXXXX	XXXXX
XXXX	[D2] mg/m ²	C1 TRT D1 / Yes	DDMMYYYY	T01	XXXXX	XXXXX	XXXXX	XXXXX	XXXXX		
				C2 TRT D1 / Yes	DDMMYYYY	T01	XXXXX	XXXXX	XXXXX	XXXXX	XXXXX
					DDMMYYYY	T01	XXXXX	XXXXX	XXXXX	XXXXX	XXXXX

<etc>

CS: Clinically Significant. Dates are displayed as DDMMYYYY, -- represents an unknown date component.

Program: (Program name.sas) (run on: DDMMYYYY HH:MM)

Filename: (Specify file name.rtf)

PROGRAMMING NOTES:

- Listing to be sorted by increasing CPX-POM dose.

Listing 16.2.4-7 - RECIST Non-Target Lesions
 (All Patients)

Center/ Patient	CPX-POM Dose group	Visit/ Non-Target Lesions Identified at Screening Visit?	Date of Scans review	Lesion Number	Organ Site	Specific Location within the Organ Site	Lymph Node Type	Method	Result		
XXXX	30 mg/m ²	C1 TRT D1 / Yes	DDMMYYYY	NT01	XXXXX	XXXXX	XXXXX	XXXXX	XXXXX		
				NT02	XXXXX	XXXXX	XXXXX	XXXXX			
XXXX	[D2] mg/m ²	C1 TRT D1 / Yes	DDMMYYYY	NT01	XXXXX	XXXXX	XXXXX	XXXXX	XXXXX		
				C2 TRT D1 / Yes	DDMMYYYY	NT01	XXXXX	XXXXX	XXXXX	XXXXX	XXXXX
					DDMMYYYY	NT02	XXXXX	XXXXX	XXXXX	XXXXX	XXXXX
XXXX	[D2] mg/m ²	C1 TRT D1 / Yes	DDMMYYYY	NT01	XXXXX	XXXXX	XXXXX	XXXXX	XXXXX		
				C2 TRT D1 / Yes	DDMMYYYY	NT01	XXXXX	XXXXX	XXXXX	XXXXX	XXXXX
					DDMMYYYY	NT01	XXXXX	XXXXX	XXXXX	XXXXX	XXXXX

<etc>

CS: Clinically Significant. Dates are displayed as DDMMYYYY, -- represents an unknown date component.

Program: (Program name.sas) (run on: DDMMYYYY HH:MM)

Filename: (Specify file name.rtf)

PROGRAMMING NOTES:

- Listing to be sorted by increasing CPX-POM dose.

Listing 16.2.4-8 - Prior and Concomitant Medications
 (All Patients)

CPX-POM Dose Group: 30 mg/m²

Center/ Patient	Type of Medication	Therapeutic Class Preferred Term Verbatim	Start Date (Day)/ End Date (Day)	Total Daily Dose (unit)/ Frequency/ Route	Reason/ Indication
XXXX		XXXXXX/ XXXXX/ XXXXXXXXXXXXX	DDMMYYYY (<-180)/ DDMMYYYY (XXX)	XXXXXXXX (XXX)/ Once/ Inhalation	XXXXXXXXXXXXX
	Conc.** Proh. [a]	XXXXXX/ XXXXX/ XXXXXXXXXXXXX	--MMYYYY/ Ongoing	Other, XXXX/ bid/ Cutaneous	XXXXXX
XXXX	Prior*	XXXXXX/ XXXXX/ XXXXXXXXXXXXX	--MMYYYY/ DDMMYYYY (XXX)	200 mg/ tid/ Other, XXXXX	XXXXXXXXXXXXXXXXXXXX

Day was from the date of first dose of CPX-POM administration. Dates are displayed as DDMMYYYY, -- represents an unknown date component.

* Prior = any medication whose end date is before the date of first dose.

** Conc. = any medication that started before the date of first dose and stopped on (or is ongoing after) the date of first dose OR any medication whose start date is either the same as (or after) the date of first dose.

[a] Proh. = Prohibited medication.

Program: (Program name.sas) (run on: DDMMYYYY HH:MM)

Filename: (Specify file name.rtf)

PROGRAMMING NOTES:

- Listing to be sorted by increasing CPX-POM dose.
- Use abbreviations or codes to present data if not enough space (and add appropriate abbreviations / codes in footnotes).

Sponsor: CicloMed
Protocol: CPX-POM-001
Statistical Analysis Plan
(TFL shells):
Version 1.0 / 02FEB2018

Protocol: CPX-POM-001

--- DELIVERY TYPE ---

Page 1 of X

Listing 16.2.5 - Drug Exposure
 (All Patients)

Center/ Patient	CPX-POM Dose group	Date of first dose administration	Visit of last dose administration	Date of last dose administration	Exposure (days)	Exposure (mg)
XXXX	30 mg/m ²	DDMMYYYY	C1 TRT D5	DDMMYYYY	XX	XX
XXXX	[D2] mg/m ²	DDMMYYYY	C2 TRT D5	DDMMYYYY	XX	XX

<cont.>

Day was from the date of first dose of CPX-POM administration. Dates are displayed as DDMMYYYY.

The CPX-POM exposure expressed in days is defined as the number of days between the first dose taken date and the last dose taken date + 1 day.

The CPX-POM exposure expressed in mg is defined as: dose per m² x Body Surface Area x CPX-POM exposure expressed in days.

Program: (Program name.sas) (run on: DDMMYYYY HH:MM)

Filename: (Specify file name.rtf)

PROGRAMMING NOTES:

- Listing to be sorted by increasing CPX-POM dose.

Listing 16.2.6-1 - Urine concentrations of CPX-POM and Metabolites
 (All Patients)

CPX-POM Dose Group: 30 mg/m²

Center/ Patient	Parameter (Unit)	Visit	Assessment Sample	Assessment Date	Assessment Time	Study Day	Urine Volume (mL)	CPX-POM Conc. (ng/mL)	CPX Conc. (ng/mL)	CPX-G Conc. (ng/mL)	
XXXX	CPX-POM (XXXX)	C1 TRT D1	Pre-Dose	DDMMMYYYY	HH:MM		XX	XX	XX	XX	
			Post-Dose [0-12]	DDMMMYYYY	HH:MM		XX	XX	XX	XX	
			Post-Dose [12-24]	DDMMMYYYY	HH:MM		XX	XX	XX	XX	
		C1 TRT D5	Post-Dose [0-12]	DDMMMYYYY	HH:MM	XX	XX	XX	XX	XX	XX
			Post-Dose [12-24]	DDMMMYYYY	HH:MM	XX	XX	XX	XX	XX	XX

Conc.: Concentration.

Study Day was from the date of first dose of CPX-POM administration. Dates are displayed as DDMMMYYYY, -- represents an unknown date component. Baseline was the last non-missing assessment prior or on the first dose date. SI units and results presented. ND = Not Done.

Program: (Program name.sas) (run on: DDMMMYYYY HH:MM)

Filename: (Specify file name.rtf)

•

Listing 16.2.6-2 - Plasma concentrations of CPX-POM and Metabolites
 (All Patients)

Replicate of Listing 16.2.6-1

Protocol: CPX-POM-001

--- DELIVERY TYPE ----

Page 1 of X

Listing 16.2.6-3 - Plasma concentrations of Biomarkers Assays
 (All Patients)

CPX-POM Dose Group: 30 mg/m²

Center/ Patient	Parameter (Unit)	Visit	Assessment Sample	Assessment Date	Assessment Time	Study Day	VEGF Conc. (pg/mL)	Percent change from Baseline	IL-6 Conc. (pg/mL)	Percent change from Baseline	IL-8 Conc. (pg/mL)	Percent change from Baseline
XXXX	CPX-POM(XXXX)	C1 TRT D1	Pre-Dose	DDMMYYYY	HH:MM		XX		XX		XX	
		C1 TRT D5	Pre-Dose	DDMMYYYY	HH:MM	XX	XX	XX.X	XX	XX.X	XX	XX.X

<repeat for Day 1 and Day 5 visits of next cycles if relevant>
<repeat for Day 22 visit of last cycle>

Conc.: Concentration.

The Baseline concentrations are the concentrations obtained at Day 1 Visit of Cycle 1.

Study Day was from the date of first dose of CPX-POM administration. Dates are displayed as DDMMYYYY, -- represents an unknown date component. Baseline was the last non-missing assessment prior or on the first dose date. SI units and results presented.

ND = Not Done.

Program: (Program name.sas) (run on: DDMMYYYY HH:MM)

Filename: (Specify file name.rtf)

PROGRAMMING NOTES:

- Repeat for all doses groups.

Listing 16.2.6-4 - PBMC Biomarkers Assays
 (All Patients)

Replicate of Listing 16.2.6-3

PROGRAMMING NOTES:

- PBMC Biomarkers are Notch 1, surviving, cyclin D, c-Myc and Hes 1 using RT-PCR.
- Repeat for all doses groups.

Protocol: CPX-POM-001

--- DELIVERY TYPE ---

Page 1 of X

Listing 16.2.6-5 - Urine beta-glucuronidase activity
 (All Patients)

CPX-POM Dose Group: 30 mg/m²

Center/ Patient	Parameter (Unit)	Visit	Assessment Sample	___Assessment___ Date Time	Study Day	Urine beta-glucuronidase activity (U/mL)
XXXX	CPX-POM (XXXX)	C1 TRT D1	Post-Dose [0-12]	DDMMYYYY HH:MM		XX
			Post-Dose [12-24]	DDMMYYYY HH:MM		XX
		C1 TRT D5	Post-Dose [0-12]	DDMMYYYY HH:MM	XX	XX
			Post-Dose [12-24]	DDMMYYYY HH:MM	XX	XX

Study Day was from the date of first dose of CPX-POM administration. Dates are displayed as DDMMYYYY, -- represents an unknown date component. Baseline was the last non-missing assessment prior or on the first dose date. SI units and results presented. ND = Not Done.

Program: (Program name.sas) (run on: DDMMYYYY HH:MM)

Filename: (Specify file name.rtf)

PROGRAMMING NOTES:

- Repeat for all doses groups.

Sponsor: CicloMed
Protocol: CPX-POM-001
Statistical Analysis Plan
(TFL shells):
Version 1.0 / 02FEB2018

Protocol: CPX-POM-001

--- DELIVERY TYPE ---

Page 1 of X

Listing 16.2.7-1 - Adverse Events
 (All Patients)

CPX-POM Dose Group: 30 mg/m²

Center/ Patient	System Organ Class/ Preferred Term/ Verbatim	Start Date (Day)/ End Date (Day)	Action Taken/ Medication or Therapies Taken?	Outcome/ Severity/ Relationship	SAE?
XXXX	XXXXXXXXXXXXXXXXXXXX/ XXXXXXXXXXXXXXXXXXXX/ XXXXXXXXXXXXXXXXXXXX	DDMMYYYY (XXX) / DDMMYYYY (XXX)	None/ No	XXXXXXXXXX/ Mild/ Not related	No
	XXXXXXXXXXXXXXXXXXXX/ XXXXXXXXXXXXXXXXXXXX/ XXXXXXXXXXXXXXXXXXXX	DDMMYYYY (XXX) / Ongoing	Dose Adjusted/ Yes	Resolved/ Moderate/ Definitely related	Yes
XXXX	XXXXXXXXXXXXXXXXXXXX/ XXXXXXXXXXXXXXXXXXXX/ XXXXXXXXXXXXXXXXXXXX	DDMMYYYY (XXX) / --MMYYYY		XXXXXXXXXX/ XXXXXX/ XXXXXX	No

<cont.>

Day was from the date of first dose of CPX-POM administration. Dates are displayed as DDMMYYYY, -- represents an unknown date component.
 MedDRA version <version #>.

Program: (Program name.sas) (run on: DDMMYYYY HH:MM)

Filename: (Specify file name.rtf)

PROGRAMMING NOTES:

- Repeat for the other CPX-POM doses by increasing order.

Sponsor: CicloMed
Protocol: CPX-POM-001
Statistical Analysis Plan
(TFL shells):
Version 1.0 / 02FEB2018

Listing 16.2.7-2 - Serious Adverse Events
(All Patients)

Replicate of Listing 16.2.7-1

PROGRAMMING NOTES:

- Repeat for the other CPX-POM doses by increasing order.
- Select all AEs where SAE = Yes.
- Remove column 'SAE' and remove SAE from footnote.

Listing 16.2.7-3 - Adverse Events Leading to Discontinuation
(All Patients)

Replicate of Listing 16.2.7-1

PROGRAMMING NOTES:

- Repeat for the other CPX-POM doses by increasing order.
- Select all AEs where action taken = permanently discontinued.

Listing 16.2.7-4 - Adverse Events Leading to Death
(All Patients)

Replicate of Listing 16.2.7-1

PROGRAMMING NOTES:

- Repeat for the other CPX-POM doses by increasing order.
- Select all AEs where outcome = Fatal

Sponsor: CicloMed
Protocol: CPX-POM-001
Statistical Analysis Plan
(TFL shells):
Version 1.0 / 02FEB2018

Protocol: CPX-POM-001

--- DELIVERY TYPE ----

Page 1 of X

Listing 16.2.8-1 - Patients Laboratory Profile: Hematology
 (All Patients)

CPX-POM Dose Group: 30 mg/m²

Center/ Patient	Visit	Assessment		Study Day	Parameter (Unit)	Normal Range	Result	CTCAE grade	Change from Baseline	Clinical Interpretation
		Date	Time							
XXXX	BAS	DDMMYYYY	HH:MM	XXX	XXXXXXXX (XXXX)	XXXXXX	XX	Grade 1		Normal
	C1 TRT D1	DDMMYYYY	HH:MM	XXX	XXXXXXXX (XXXX)	XXXXXX	XX L/H	Grade 2	XXXX	Abnormal, NCS
	C1 TRT D4	DDMMYYYY	HH:MM	XXX	XXXXXXXX (XXXX)	XXXXXX	XX L/H	Grade 2	XXXX	Abnormal, NCS
	C1 TRT D10	DDMMYYYY	HH:MM	XXX	XXXXXXXX (XXXX)	XXXXXX	XX L/H	Grade 3	XXXX	Abnormal, CS

<for Cycle 2 to last-1 cycle, repeat for Day 1 visit and Day 4 visit if relevant>
<for the last cycle, repeat also for Day 22 visit and Day 28 visit>

Study Day was from the date of first dose of CPX-POM administration. Dates are displayed as DDMMYYYY, -- represents an unknown date component. Baseline was the last non-missing assessment prior or on the first dose date. SI units and results presented. L/H = low/high value based upon normal ranges. R = repeat/unscheduled assessments. CS = Clinically Significant; NCS = Not Clinically Significant; ND = Not Done.

Program: (Program name.sas) (run on: DDMMYYYY HH:MM)

Filename: (Specify file name.rtf)

PROGRAMMING NOTES:

- Repeat for the other CPX-POM doses by increasing order.

Sponsor: CicloMed
Protocol: CPX-POM-001
Statistical Analysis Plan
(TFL shells):
Version 1.0 / 02FEB2018

Listing 16.2.8-2 - Patients Laboratory Profile: Clinical Chemistry
(All Patients)

Replicate of Listing 16.2.8-1

PROGRAMMING NOTES:

- Listing to be sorted by increasing order.

Listing 16.2.8-3 - Patients Laboratory Profile: Coagulation and Thyroid Panel
(All Patients)

Replicate of Listing 16.2.8-1

PROGRAMMING NOTES:

- Listing to be sorted by increasing order.
- Only Day 1 of each cycle.

Listing 16.2.8-4 - Patients Laboratory Profile: Urinalysis
(All Patients)

Replicate of Listing 16.2.8-1

PROGRAMMING NOTES:

- Listing to be sorted by increasing order.
- Replace 'Day 4' by 'Day 5' for each cycle.

Sponsor: CicloMed
Protocol: CPX-POM-001
Statistical Analysis Plan
(TFL shells):
Version 1.0 / 02FEB2018

Protocol: CPX-POM-001

--- DELIVERY TYPE ---

Page 1 of X

Listing 16.2.8-5 - Vital Signs
 (All Patients)

CPX-POM Dose Group: 30 mg/m²

Center/ Patient	Visit	Assessment		Study Day	Parameter (unit)	Position	Result	Change from Baseline
		Date	Time					
XXXX	BAS	DDMMYYYY	HH:MM	XXX	Pulse Rate (bpm)	Supine	XXX +	
					Respiratory Rate (bpm)	Supine	XXX	
					Systolic BP (mmHg)	Supine	XXX	
					Diastolic BP (mmHg)	Supine	XXX	
					Oxygen Saturation (mmHg)		XXX	
					Body Weight (kg)		XXX.X	
					Temperature (C)		XX.X	
	C1 TRT D2	DDMMYYYY	HH:MM	XXX	Pulse Rate (bpm)	Supine	XXX +	XX
					Respiratory Rate (bpm)	Supine	XXX	XX
					Systolic BP (mmHg)	Supine	XXX	XX
					Diastolic BP (mmHg)	Supine	XXX	XX
					Oxygen Saturation (mmHg)		XXX	XX
					Body Weight (kg)		XXX.X	X.X
					Temperature (C)		XX.X	X.X

<repeat for Day 3, Day 4, Day 5, Day 6 and Day 10 visits of Cycle 1>
 <for Cycle 2 to last-1 cycle, repeat from Day 1 to Day 6 visits if relevant>
 <for the last cycle, repeat also for Day 22 visit and Day 28 follow-up visit>

Study Day was from the date of first dose of CPX-POM administration. Dates are displayed as DDMMYYYY. Baseline was the last non-missing assessment prior or on the first dose.

+ Results of clinical importance (see SAP). BP = Blood Pressure; bpm = beats per minute; ND = Not Done.

Program: (Program name.sas) (run on: DDMMYYYY HH:MM)

Filename: (Specify file name.rtf)

PROGRAMMING NOTES:

- Repeat for all doses groups

Sponsor: CicloMed
Protocol: CPX-POM-001
Statistical Analysis Plan
(TFL shells):
Version 1.0 / 02FEB2018

Protocol: CPX-POM-001

--- DELIVERY TYPE ----

Page 1 of X

Listing 16.2.8-6 - ECG Results and Interpretation
 (All Patients)

CPX-POM Dose Group: 30 mg/m²

Center/ Patient	Visit	Assessment Date (Day)	Parameter (unit)	Clinician Interpretation	Result	Change from baseline
XXXX	BAS	DDMMYYYY (XXX)	Heart Rate (bpm)	Normal	XXX	
			PR interval (msec)	Normal		
			QRS duration (msec)	Normal		
			QT interval (msec)	Normal		
			QTcB interval (msec)	Normal		
			QTcF interval (msec)	Normal		
			C1 TRT D5	DDMMYYYY (XXX)		
PR interval (msec)	Normal					
QRS duration (msec)	Normal					
QT interval (msec)	Normal					
QTcB interval (msec)	Abnormal, Not Clinical Significant	XXX +				
QTcF interval (msec)	Abnormal, Not Clinical Significant	XXX +				

<for Cycle 2 to last-1 cycle, repeat for Day 1 visit if relevant>
<for the last cycle, repeat also for Day 28 follow-up visit>

Day was from the date of first dose of CPX-POM administration. Dates are displayed as DDMMYYYY. Baseline was the last non-missing assessment prior or on the first dose date.

QTcB and QTcF: +: >450 msec; ++: > 480 msec; +++: >500 msec; *: > 30 msec above baseline; **: > 60 msec above baseline.

R = repeated/ unscheduled assessment.

Program: (Program name.sas) (run on: DDMMYYYY HH:MM)

Filename: (Specify file name.rtf)

PROGRAMMING NOTES:

- Repeat for all dose groups.

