| CPX-POM infusions ²⁴ | | X | X | X | X | X | | | | |

Abbreviations: ALP = alkaline phosphatase; ALT = alanine aminotransferase; aPTT = activated partial thromboplastin time; AST = aspartate aminotransferase; BSA = body surface area; BUN = blood urea nitrogen; CPX-POM = ciclopirox phosphoryloxymethyl ester; CT = computed tomography; D = day; ECG = electrocardiogram; ECOG = Eastern Cooperative Oncology Group; EDTA = ethylenediamine tetraacetic acid; eGFR = estimated glomerular filtration rate; GGT = gamma glutamyl transferase; HIV = human immunodeficiency virus; IV = intravenous; MUGA = multi-gated acquisition; MRI = magnetic resonance imaging; PBMC = peripheral blood mononuclear cell; PD = pharmacodynamic; PK = pharmacokinetic; PT = prothrombin time; RBC = red blood cell; T3 = triiodothyronine; T4 = thyroxine; TSH = thyroid stimulating hormone; V = visit; WBC = white blood cell.

1. On Days 1 and 5 of Cycle 1, patients will be required to stay at the clinical research unit for at least 12 hours for PK sampling and other assessments. If patients are unable or unwilling to attend the required 12 hours of clinic visitation required for steady-state PK sampling on Day 5 of Cycle 1, the steady-state PK sampling may be postponed to Day 5 of Cycle 2. To shorten the duration of the Cycle 1, Day 1 visit, if needed, the safety laboratory blood samples required for this visit may be drawn up to 3 days before Day 1.
2. The Day 10 (Visit 8) study visit will only be required during Cycle 1.
3. After cycle 1; visit windows can be considered on a case by case basis due to events such as holidays; Cycle 1 needs to occur without visit windows. D6 can occur +2 calendar days for cycles after Cycle 1 is completed.
4. If final treatment cycle, patient returns for assessments on Day 22. If additional cycles are planned, patient skips this visit and restarts schedule at Day 1 (except for PK). Patients may continue to receive cycles of CPX-POM until progression of disease, intolerable toxicity occurs, or another withdrawal criterion applies.

5. The Follow-up visit will occur 28±5 days after the last dose of CPX-POM administered during the last treatment cycle. Or, in the event that a patient discontinues from the study prematurely, the site will make every effort to perform the assessments listed for this study visit.
6. Hepatitis screening will include tests for Hepatitis A, Hepatitis B, and Hepatitis C.

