- Grade 4 absolute neutrophil count (ANC) greater than 5 days
- Febrile neutropenia
- Grade ≥ 3 non-hematologic toxicity of any duration, except:
 - Grade 3 nausea, vomiting, or diarrhea and Grade 4 vomiting or diarrhea in the absence of maximal medical therapy that resolves in 72 hours
 - Grade 3 fatigue lasting < 5 days
 - Grade 3 hypertension that can be controlled with medical therapy
 - An increase of indirect (unconjugated) bilirubin indicative of M. Meulengracht/Gilbert's syndrome
 - Serum lipase and/or serum amylase CTCAE Grade 3 ≤ 7 consecutive days without clinical signs or symptoms of pancreatitis
- Delay in study drug due to toxicity for > 2 weeks
- alanine aminotransferase (ALT)/aspartate aminotransferase (AST) $> 3x$ the upper limit of normal (ULN) with bilirubin $> 2x$ ULN without another explanation (e.g., cholestasis)
- Any patient who is unable to receive 80% of the expected doses of CPX-POM (i.e., patients who are unable to receive at least 4 of the 5 scheduled doses) in Cycle 1 because of AEs will be considered to have a DLT.

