4.5. End of Study Definition

A patient is considered to have completed the study if he/she has completed the first cycle of the study.

The end of the study is defined as the date of the last procedure for the last patient in the study. At the end of the study the patient will complete the D22 visit as well as the Follow-Up Visit.

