7. DISCONTINUATION OF STUDY INTERVENTION AND PATIENT DISCONTINUATION/WITHDRAWAL

7.1. Discontinuation of Study Treatment

Treatment should be discontinued for a DLT until the toxicity is resolved. If treatment is reinitiated, then the dose of CPX-POM should be reduced as described in Section 6.1.5. If a patient has a second episode of the same DLT despite dose reduction, he or she should be removed from study as outlined in Table 1. Schedule of Assessments (complete D22 and the Early Termination Visit).

In the event of discontinuation of CPX-POM, every effort should be made to complete the assessments that are scheduled for the Follow-up/Early Termination visit. See the Schedule of Assessments (Table 1) for data to be collected at the time of early termination.

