Listing 16.2.8-4 – Patients Laboratory Profile: Urinalysis (All Patients)	78
Listing 16.2.8-5 – Vital Signs (All Patients)	79
Listing 16.2.8-6 – ECG Results and Interpretation (All Patients)	80

Table 14.1-1 - Patients disposition
 (All patients)

Cycle	CPX-POM 30 mg/m ² N=1 n (%)	CPX-POM [D2] mg/m ² N=X n (%)	CPX-POM [D3] mg/m ² N=X n (%)	CPX-POM [D4] mg/m ² N=X n (%)	CPX-POM [D5] mg/m ² N=X n (%)	CPX-POM [D6] mg/m ² N=X n (%)	CPX-POM [D7] mg/m ² N=X n (%)
Cycle 1							
Treated	XX (XX.X)	XX (XX.X)	XX (XX.X)	XX (XX.X)	XX (XX.X)	XX (XX.X)	XX (XX.X)
Completed the cycle [a]	XX (XX.X)	XX (XX.X)	XX (XX.X)	XX (XX.X)	XX (XX.X)	XX (XX.X)	XX (XX.X)
Discontinued from the cycle	XX (XX.X)	XX (XX.X)	XX (XX.X)	XX (XX.X)	XX (XX.X)	XX (XX.X)	XX (XX.X)
Reason for discontinuation from the cycle							
Dose Limiting Toxicity	XX (XX.X)	XX (XX.X)	XX (XX.X)	XX (XX.X)	XX (XX.X)	XX (XX.X)	XX (XX.X)
Withdrawn Consent	XX (XX.X)	XX (XX.X)	XX (XX.X)	XX (XX.X)	XX (XX.X)	XX (XX.X)	XX (XX.X)
Physician Decision	XX (XX.X)	XX (XX.X)	XX (XX.X)	XX (XX.X)	XX (XX.X)	XX (XX.X)	XX (XX.X)
Death	XX (XX.X)	XX (XX.X)	XX (XX.X)	XX (XX.X)	XX (XX.X)	XX (XX.X)	XX (XX.X)
Lost to Follow-up	XX (XX.X)	XX (XX.X)	XX (XX.X)	XX (XX.X)	XX (XX.X)	XX (XX.X)	XX (XX.X)

Percentages are based on the number of patients enrolled.

[a] A patient completed Cycle 1 if s/he attended visit Day 10 (if Cycle 1 was not the last cycle) or Visit Day 22 (if Cycle 1 was the last cycle).

Program: (Program name.sas) (run on: DDMMYYYY HH:MM)

Filename: (Specify file name.rtf)

Table 14.1-1 - Patients disposition
 (All patients)

Cycle	CPX-POM 30 mg/m ² N=1 n (%)	CPX-POM [D2] mg/m ² N=X n (%)	CPX-POM [D3] mg/m ² N=X n (%)	CPX-POM [D4] mg/m ² N=X n (%)	CPX-POM [D5] mg/m ² N=X n (%)	CPX-POM [D6] mg/m ² N=X n (%)	CPX-POM [D7] mg/m ² N=X n (%)
Cycle 2							
Treated	XX (XX.X)	XX (XX.X)	XX (XX.X)	XX (XX.X)	XX (XX.X)	XX (XX.X)	XX (XX.X)
Completed the cycle [b]	XX (XX.X)	XX (XX.X)	XX (XX.X)	XX (XX.X)	XX (XX.X)	XX (XX.X)	XX (XX.X)
Discontinued from the cycle	XX (XX.X)	XX (XX.X)	XX (XX.X)	XX (XX.X)	XX (XX.X)	XX (XX.X)	XX (XX.X)
Reason for discontinuation from the cycle							
Dose Limiting Toxicity	XX (XX.X)	XX (XX.X)	XX (XX.X)	XX (XX.X)	XX (XX.X)	XX (XX.X)	XX (XX.X)
Withdrawn Consent	XX (XX.X)	XX (XX.X)	XX (XX.X)	XX (XX.X)	XX (XX.X)	XX (XX.X)	XX (XX.X)
Physician Decision	XX (XX.X)	XX (XX.X)	XX (XX.X)	XX (XX.X)	XX (XX.X)	XX (XX.X)	XX (XX.X)
Death	XX (XX.X)	XX (XX.X)	XX (XX.X)	XX (XX.X)	XX (XX.X)	XX (XX.X)	XX (XX.X)

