Lost to Follow-up	XX (XX.X)	XX (XX.X)	XX (XX.X)	XX (XX.X)	XX (XX.X)	XX (XX.X)	XX (XX.X)

<repeat until last-1 cycle>

Percentages are based on the number of patients enrolled.

[b] A patient completed Cycle 2 (or any next cycle until last-1 cycle) if s/he attended visit Day 6 (if Cycle 2 or any next cycle was not the last cycle) or Visit Day 22 (if Cycle 2 or any next cycle was the last cycle).

Program: (Program name.sas) (run on: DDMMYYYY HH:MM)

Filename: (Specify file name.rtf)

Table 14.1-1 - Patients disposition
 (All patients enrolled)

Cycle	CPX-POM 30 mg/m ² N=1 n (%)	CPX-POM [D2] mg/m ² N=X n (%)	CPX-POM [D3] mg/m ² N=X n (%)	CPX-POM [D4] mg/m ² N=X n (%)	CPX-POM [D5] mg/m ² N=X n (%)	CPX-POM [D6] mg/m ² N=X n (%)	CPX-POM [D7] mg/m ² N=X n (%)
Last Cycle							
Treated	XX (XX.X)	XX (XX.X)	XX (XX.X)	XX (XX.X)	XX (XX.X)	XX (XX.X)	XX (XX.X)
Completed the cycle [c]	XX (XX.X)	XX (XX.X)	XX (XX.X)	XX (XX.X)	XX (XX.X)	XX (XX.X)	XX (XX.X)
Discontinued from the cycle	XX (XX.X)	XX (XX.X)	XX (XX.X)	XX (XX.X)	XX (XX.X)	XX (XX.X)	XX (XX.X)
Reason for discontinuation from the cycle							
Dose Limiting Toxicity	XX (XX.X)	XX (XX.X)	XX (XX.X)	XX (XX.X)	XX (XX.X)	XX (XX.X)	XX (XX.X)
Withdrawn Consent	XX (XX.X)	XX (XX.X)	XX (XX.X)	XX (XX.X)	XX (XX.X)	XX (XX.X)	XX (XX.X)
Physician Decision	XX (XX.X)	XX (XX.X)	XX (XX.X)	XX (XX.X)	XX (XX.X)	XX (XX.X)	XX (XX.X)
Death	XX (XX.X)	XX (XX.X)	XX (XX.X)	XX (XX.X)	XX (XX.X)	XX (XX.X)	XX (XX.X)
Lost to Follow-up	XX (XX.X)	XX (XX.X)	XX (XX.X)	XX (XX.X)	XX (XX.X)	XX (XX.X)	XX (XX.X)
Attended the follow-up visit (Day 28)	XX (XX.X)	XX (XX.X)	XX (XX.X)	XX (XX.X)	XX (XX.X)	XX (XX.X)	XX (XX.X)

Percentages are based on the number of patients enrolled.
 [c] A patient completed the Last Cycle if s/he attended visit Day 22.

Program: (Program name.sas) (run on: DDMMYYYY HH:MM)

Filename: (Specify file name.rtf)

PROGRAMMING NOTES:

- Display all the reasons for discontinuation where there is at least one patient within that category

Table 14.1-2 - Number (%) of Patients in the Analysis Populations
 (All patients)

	CPX-POM 30 mg/m ² N=1 n (%)	CPX-POM [D2] mg/m ² N=X n (%)	CPX-POM [D3] mg/m ² N=X n (%)	CPX-POM [D4] mg/m ² N=X n (%)	CPX-POM [D5] mg/m ² N=X n (%)	CPX-POM [D6] mg/m ² N=X n (%)	CPX-POM [D7] mg/m ² N=X n (%)
Safety Population	XX (XX.X)	XX (XX.X)	XX (XX.X)	XX (XX.X)	XX (XX.X)	XX (XX.X)	XX (XX.X)
Efficacy Population	XX (XX.X)	XX (XX.X)	XX (XX.X)	XX (XX.X)	XX (XX.X)	XX (XX.X)	XX (XX.X)

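### SAP Table 14.1-1 defines completing a cycle by visit attendance, so a patient who stops dosing early for a DLT but attends the visit counts as completed and can drop out of the DLT reason row

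*SAP*

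**What the plan says.** SAP Table 14.1-1 has a block for each cycle, by dose group, with rows for patients treated, completed and discontinued. Completion is set by three footnotes:

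- Cycle 1: "A patient completed Cycle 1 if s/he attended visit Day 10 (if Cycle 1 was not the last cycle) or Visit Day 22" when Cycle 1 was the last cycle.
- Cycle 2 up to the cycle before the last: the patient "attended visit Day 6 (if Cycle 2 or any next cycle was not the last cycle"), or Day 22 if it was the last.
- Last cycle: "A patient completed the Last Cycle if s/he attended visit Day 22".

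None of them mentions doses received. Reasons appear only in a block headed "Reason for discontinuation from the cycle", and DLT is one of the reasons named there. The row for discontinuation from the cycle has no footnote and no definition.

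The protocol sends patients to the visit that decides completion. Table 1, footnote 4: "If final treatment cycle, patient returns for assessments on Day 22". Section 4.5: "At the end of the study the patient will complete the D22 visit as well as the Follow-Up Visit". Section 7.1, on a patient removed after a second episode of the same DLT: "complete D22 and the Early Termination Visit".

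Protocol Section 4.1 also makes an early stop in Cycle 1 a DLT in itself. It classes as DLTs "patients who are unable to receive at least 4 of the 5 scheduled doses" because of adverse events.

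**The concern.** A disposition table should show, by dose, how many patients received the treatment as planned and why the others did not. This one records who came to a visit. The two differ most for patients who stop dosing because of toxicity and then stay in follow-up as the protocol asks. The better such patients are followed, the more of them are recorded as completing the cycle.

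The DLT reason row matters here because it is the only DLT count in the shells supplied. Protocol Section 9.5.1 says that DLTs will be listed and summarised by dose group, but no shell is a DLT table and none carries a DLT flag. A reader looking for DLTs by dose in the planned outputs would come to this row.

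**Working it through.** The plan states no figure on this point, so there is none to reproduce. The check traces patients through the rules and then counts a hypothetical cohort.

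**Tracing patients**

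1. *Cycle 1 is the last cycle.* A patient receives 2 of 5 doses and stops because of an adverse event. Since 2/5 = 40% is below the 4/5 = 80% in Section 4.1, this is a DLT. The patient returns on Day 22 under Table 1, footnote 4. The Cycle 1 and last-cycle footnotes are both met, so the patient is completed.
2. *Dosing resumes later.* Section 6.1.5 allows treatment to restart after a DLT resolves. If the same patient goes on to Cycle 2, Day 10 attendance is enough to complete Cycle 1.
3. *The reverse case.* A patient receives all 5 doses in a last cycle and misses only Day 22. The completion rule is not met, although treatment was given in full.

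In cases 1 and 2 the patient counts as completed however the discontinued row is read. Loss from the DLT reason row needs one further assumption: that completed and discontinued are exclusive.

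**Counting**

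Take n treated patients in their last cycle. Of these, d stop dosing early for a DLT, and a of those d attend Day 22. The other n − d receive all doses and attend. Treat the two categories as exclusive.

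- Attendance rule: completed = n − (d − a); DLT row = d − a.
- Dosing rule: completed = n − d; DLT row = d.
- Under-count in the DLT row = d − (d − a) = a.

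Cohort sizes 3 and 6 are those of the protocol's standard escalation scheme. The values of d and a are illustrations, not trial figures.

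| n | d | a | Attendance rule: completed | Attendance rule: DLT row | Dosing rule: completed | Dosing rule: DLT row |
|---|---|---|---|---|---|---|
| 6 | 2 | 2 | 6 (100.0%) | 0 (0.0%) | 4 (66.7%) | 2 (33.3%) |
| 6 | 2 | 1 | 5 (83.3%) | 1 (16.7%) | 4 (66.7%) | 2 (33.3%) |
| 6 | 2 | 0 | 4 (66.7%) | 2 (33.3%) | 4 (66.7%) | 2 (33.3%) |
| 3 | 1 | 1 | 3 (100.0%) | 0 (0.0%) | 2 (66.7%) | 1 (33.3%) |

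The two rules agree only when no early DLT stopper attends.

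**Where else the information appears**

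- Listing 16.2.1-2 has a reason for discontinuation and a last-dose date for each patient.
- Table 14.3-1.1 (by dose group), Table 14.3-1.6 (by system organ class and preferred term) and Listing 16.2.7-3 report adverse events leading to discontinuation. They use the action taken, not attendance.
- None of these flags a DLT. A DLT after which dosing resumes is not a permanent discontinuation, so the action-taken outputs would not select it.

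**The case against.** A reader might infer that the reason for stopping disappears from the report, or that toxicity stops are under-counted throughout. The documents do not support that. Individual reasons have a column in Listing 16.2.1-2, and permanent discontinuations for adverse events are tabulated independently of Day 22.

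A reader might also infer that escalation or the MTD is affected. It is not. Sections 4.1 and 9.8 place dose decisions with the Safety Review Committee, and Section 9.5.1 defines the MTD by DLT counts, not by disposition.

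Nor does it follow that most patients are misclassified because all of them stop eventually. A patient who receives every dose, attends Day 22 and then stops for progression did complete that cycle. For that patient the gap is narrower: progression is not a named reason, and the reasons sit only under discontinuation from the cycle. The programming note to display any reason with at least one patient may let further reasons in, but it does not move a completed patient into the discontinued branch.

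Three further points have force.

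- Attendance is a sensible marker of finishing the DLT observation period, since Section 4.1 requires follow-up through Day 22 or Cycle 2 Day 1. That justifies reporting attendance, but not labelling it completion of the cycle beside reasons for stopping.
- The Day 22 duty is not uniform. Section 7.1 names it for a repeat DLT; for other discontinuations, Sections 7.1 and 7.2 ask for the Follow-up/Early Termination visit. Table 1, footnote 4 and Section 4.5 still place Day 22 in a final cycle.
- Exclusivity is not stated, and the document is headed as table, figure and listing shells. Narrative SAP text could define these terms.

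**Conclusion.** The point holds for the by-dose disposition summary. As the footnotes stand, an early DLT stopper who attends the deciding visit is counted as having completed the cycle; this needs no assumption. If the categories are exclusive, the DLT row is short by exactly the number of such attendees: in the example of 6, it shows 0 where 2 belong.

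The documents give no attendance rate among patients who stop, so the expected number misclassified cannot be estimated. The conclusion rests on the shells alone and would change if narrative SAP text, not supplied, defined completion or discontinuation differently. The table should be corrected, but the fault is one of reporting: it bears on how tolerability by dose will read, not on how doses are chosen.

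**What to change.** Change the shell of Table 14.1-1 and its footnotes:

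1. Define *Completed* and *Discontinued from the cycle* by dosing (all scheduled doses in the cycle received, yes or no), and state that they are exclusive. Referring to scheduled doses keeps the rule valid if the committee changes the dosing schedule.
2. Show a reason for every patient who stops dosing early in a cycle or stops CPX-POM permanently, including one who stops after a fully dosed cycle. Name disease progression and non-DLT adverse event among the reasons.
3. Report Day 22 attendance in its own row, beside the existing follow-up attendance row.

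The data are already planned for display: dosing in Listing 16.1.7-1, and reason and last-dose date in Listing 16.2.1-2. The cost is shell and footnote wording plus the matching programming. If narrative SAP text exists, align its definitions at the same time.

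The corrected row will count dosing stops for DLT, not all DLTs, because a DLT can arise after the last dose of a cycle. It does not replace the DLT summary promised in protocol Section 9.5.1.
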